### 4.4 Handling of measurements obtained at the EW visit

Subjects withdrawing early from the study should undergo the same assessments scheduled for the Week 48 visit as soon as possible after withdrawal (as an EW visit) and then enter the SFU Period, completing study participation with the SFU Visit 20 weeks after their final dose of IMP.

The following rules will apply with regard to the inclusion of the results obtained at the EW visit in the descriptive summaries:

- Any measurements conducted at the EW visit should be included in the summaries for the respective scheduled visit, if the EW visit occurs at the time of the next scheduled visit. For example, if the EW visit occurs on Day 42, the results would be summarized together with the Visit 6 (Week 6, Day 42) results
- If the EW visit does not correspond to the day of a scheduled visit, the assessments of the EW visit should be mapped to the nearest scheduled visit, relative to the Baseline visit date, following the last scheduled visit where assessments are available
- If the date of the EW visit is equidistant between 2 scheduled visits at which no scheduled assessments were performed, the assessments from the EW visit will be mapped to the earliest of these visits
- If an EW visit mapping results in data being mapped to a visit where the specific assessment is not actually collected per the protocol schedule of assessments, these data will not be included in the summary statistics and will be listed only
- The only exception to the above rule is for ADA (for both BKZ and CZP) assessments, in which all early withdrawal visit assessments will be assigned to the next scheduled visit at which ADA are assessed. The rationale for this is that ADA positivity is summarized over a given study period. As part of that summary, a table indicating the first visit at which ADA positivity is observed will be presented. In order to match the number of subjects who were ADA positive at specific visits with the overall positivity for the period, it is necessary to ensure that ADA positivity is attributed to a visit where ADA antibody assessments were performed

Assessments from the EW visit will be displayed as the mapped visit and will be flagged in the by-visit data listings.

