9. Subject has active suicidal ideation as indicated by a positive response (“Yes”) to Questions 4 or 5 or to the suicidal behavior questions of the “Since Last Visit” version of the self-rated C-SSRS. The subject should be referred immediately to a Mental Healthcare Professional and must be withdrawn from the study.

10. Subjects with a Hospital Anxiety and Depression Scale—Depression (HADS-D) score ≥ 15 must be withdrawn. Any subject who develops a HADS-D score of ≥ 10 during the study should be referred immediately to a Mental Healthcare Professional for further evaluation and potential withdrawal by the Investigator.

11. Subjects with newly diagnosed IBD or with IBD flares during the study must:

- Be referred, as appropriate, to a health care professional treating IBD, such as a gastroenterologist
- Discontinue IMP and be followed-up until resolution of active IBD symptoms

If IBD flares increase in severity or frequency during the study, the Investigator should use clinical judgement in deciding whether the subject should continue in the study and contact the Medical Monitor and UCB study physician to confirm the subject’s suitability for continued participation in the study.

In an attempt to prevent missing data during the study, efforts will be made to collect data from subjects who withdraw early from the study (NRC, 2010). If a subject withdraws from study treatment for any of the above criteria prior to Week 48, they will be asked to return for the study termination assessments as laid down at the Week 48/WD Visit and for the SFU Visit (20 weeks after final dose administration). All subjects who withdraw from the study due to an AE must be followed until resolution of the event or until the event is considered stable. All subjects who withdraw from the study due to development of a laboratory abnormality must be closely monitored. If a subject at any time has had an ALT and/or AST >5 xULN, additional monitoring of hepatic markers will be performed every week or 2 weeks until resolution of the event, the event is considered stable, or they have reached the end of the SFU Period.

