8.8 Week 12 (Visit 8)

- Record concomitant medications.
- Assess adverse events.
- C-SSRS.
- HADS.
- Determine the BASDAI.
- Determine the BASFI.

- Perform the PGADA.
- Perform the PhGADA.
- Total and nocturnal spinal pain (NRS).
- Perform a physical examination, including an evaluation for signs and symptoms of active TB and risk for exposure to TB and weight.
- Measure vital signs (temperature, pulse, and blood pressure).
- Perform a 12-lead ECG.
- Administer the tuberculosis questionnaire.
- Perform a urine pregnancy test.
- Collect samples for:
 - Hematology/biochemistry/urinalysis.
 - Bimekizumab and CZP plasma concentrations.
 - Anti-bimekizumab and anti-CZP antibody detection.
 - hs-CRP.
- If the respective ICF has been provided collect blood samples for:
 - Cytokines, complement, and biomarker analyses.
 - Pharmacogenetic variables.
 - Nonhereditary pharmacogenomic variables.
- Collect urine samples for biomarker research if the respective ICF has been provided.
- Perform a PET-MRI or PET-CT scan in at least 25 subjects at selected sites within 2 weeks after Week 12 Visit if PET-positive lesions were observed in the previous scan.
- Administer IMP.
- Record visit in the IRT.

8.9 Week 16 (Visit 9), Week 20 (Visit 10), Week 28 (Visit 12), Week 32 (Visit 13), Week 40 (Visit 15), and Week 44 (Visit 16)

- Record concomitant medications.
- Assess adverse events.
- C-SSRS.
- HADS.
- Determine the BASDAI.
- Determine the BASFI.
- Perform the PGADA.

- Perform the PhGADA.
- Total and nocturnal spinal pain (NRS).
- Measure vital signs (temperature, pulse, and blood pressure).
- Perform a 12-lead ECG.
- Blood sample for hs-CRP.
- Perform a urine pregnancy test.
- Administer IMP.
- Record visit in the IRT.

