8.11 Week 48 (Visit 17)/Early Withdrawal Visit

- Record prior and concomitant medications.
- Assess adverse events.
- C-SSRS.
- HADS.
- Determine the BASDAI.
- Determine the BASFI.
- Perform the PGADA.
- Perform the PhGADA.
- Total and nocturnal spinal pain (NRS).
- Measure vital signs (temperature, pulse, and blood pressure).
- Perform a 12-lead ECG.
- Perform a physical examination, including an evaluation for signs and symptoms of active TB and risk for exposure to TB and weight.
- Perform a 12-lead ECG.
- Administer the tuberculosis questionnaire.
- Perform an IGRA tuberculosis test (QuantiFERON TB test).
- Perform a urine pregnancy test.
- Collect samples for:
 - Hematology/biochemistry/urinalysis.
 - Bimekizumab and CZP plasma concentrations.
 - Anti-bimekizumab and anti-CZP antibody detection.
 - hs-CRP.

- If the respective ICF has been provided collect blood samples for:
 - Cytokines, complement, and biomarker analyses.
 - Pharmacogenetic variables.
 - Nonhereditary pharmacogenomic variables.

- Collect urine samples for biomarker research if the respective ICF has been provided.
- Obtain a X-ray or CT scan of the chest if the QuantiFERON TB test returned a positive result.
- Perform a PET-MRI or PET-CT scan in at least 25 subjects at selected sites within 2 weeks after the Week 48/WD Visit if PET-positive lesions were observed in the previous scan. At the WD Visit, the PET-MRI or PET-CT must be done only, if the previous imaging evaluation occurred more than 12 weeks ago and if PET-positive lesions were observed in the previous scan.
- Record visit in the IRT.

8.12 Safety Follow-Up Visit (Week 64, Visit 18, 20 weeks after the final dose of IMP)

- Record concomitant medications.
- Assess adverse events.
- Measure vital signs (temperature, pulse, and blood pressure).
- Perform a 12-lead ECG.
- Administer the tuberculosis questionnaire.
- Perform a urine pregnancy test.
- Collect samples for:
 - Hematology/biochemistry/urinalysis.
 - Bimekizumab and CZP plasma concentrations.
 - Anti-bimekizumab and anti-CZP antibody detection.
 - hs-CRP.
- If the respective ICF has been provided collect blood samples for:
 - Cytokines, complement, and biomarker analyses.
 - Nonhereditary pharmacogenomic variables.
- Record visit in the IRT.

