### **11.3 Clinical laboratory evaluations**

Laboratory data (chemistry, hematology, and urinalysis) and changes from Baseline (if applicable) for numeric variables will be listed by treatment group and visit. Any laboratory variables that are BLQ or ALQ will be handled as described in [Section 4.2.3](#). Values outside the reference range for the numeric variables will be flagged in the listings and, in addition, will be listed separately. The reference ranges will also be reported in the listings.

Chemistry and hematology variables presented in [Table 11-1](#) will be summarized by treatment group at each visit, for both observed values and changes from Baseline. Figures of mean and mean change from Baseline will be presented by treatment for the absolute neutrophil count (ANC). All treatment groups will be overlaid on the same plot and the plot will include the error bars based on the SD (ie, mean +/-SD).

Laboratory variables will be grouped according to the laboratory function panel and categorized as normal, high or low, if applicable, based on the reference range supplied by the analytical laboratory. For selected variables that are identified in [Table 11-1](#), the change in category from Baseline will be presented in shift tables at all post-Baseline visits.

The number and percentage of subjects with treatment-emergent markedly abnormal (TEMA) values will be tabulated by treatment group and visit. Markedly abnormal laboratory values will generally be defined as those categorized as Grade 3 or Grade 4 as per the Rheumatology Common Toxicity Criteria (RCTC). Communication with the lead author of the RCTC publication has revealed that the reference ranges for absolute lymphocyte counts (ALC) are in error, therefore ALC criteria will follow the ranges defined as per the Common Terminology Criteria for Adverse Events (CTCAE) Version 4.03 (United States Department of Health and Human Services, 2010). Additional laboratory variables (not present in the RCTC publication) will also be categorized as per the CTCAE Version 4.03. The criteria for identifying TEMA values are presented in [Table 14-5](#) and [Table 14-6](#) for hematology and chemistry values respectively.

Laboratory measurements meeting the criteria for TEMA will be listed separately for hematology and chemistry. The listings will include all measurements for any variable with at least one TEMA result for each subject.

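### SAP 4.4 lists but does not summarise some early-withdrawal results: laboratory values in 6 of 9 extension visit slots, and withdrawal PET-CT scans in 5 of 6

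*SAP*

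**What the plan says.** **Mapping and exclusion.** Under SAP 4.4, an EW visit that does not fall on a scheduled visit day is "mapped to the nearest scheduled visit, relative to the Baseline visit date, following the last scheduled visit where assessments are available". If the test is not collected at that visit under the protocol schedule, "these data will not be included in the summary statistics and will be listed only". The SAP adds: "The only exception to the above rule is for ADA". For ADA, "all early withdrawal visit assessments will be assigned to the next scheduled visit at which ADA are assessed".

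**Laboratory schedule.** In protocol Table 5-1 and sections 8.3 to 8.11, haematology, biochemistry and urinalysis are drawn at every Treatment Period visit. In the extension they are drawn only at Weeks 24, 36 and 48/WD. SAP 11.3 says: "The number and percentage of subjects with treatment-emergent markedly abnormal (TEMA) values will be tabulated by treatment group and visit".

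**PET schedule.** After Baseline, scans are planned at Week 12 and Week 48/WD. Protocol 8.11 limits the withdrawal scan: "At the WD Visit, the PET-MRI or PET-CT must be done only, if the previous imaging evaluation occurred more than 12 weeks ago". The previous scan must also have shown PET-positive lesions. SAP 8.3.6.2 names three time points (Baseline, Week 12 and Week 48) and gives no rule for a withdrawal scan.

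**Purpose of the withdrawal assessments.** Protocol 6.3: "In an attempt to prevent missing data during the study, efforts will be made to collect data from subjects who withdraw early".

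**The concern.** The protocol asks withdrawing subjects for a further laboratory draw and, where eligible, a further PET scan, in order to limit missing data. The SAP then tests each result against the schedule of the visit to which it happens to be mapped. For tests on a sparse extension schedule, most visits fail that test, and the result appears only in a listing.

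Two sets of summaries are exposed. Safety is the only secondary objective, and TEMA counts are its main laboratory table. A markedly abnormal haematology value found at an EW visit in most extension slots would have no row in that table. For bone formation, the Week 48 SUVauc and lesion-count summaries would describe mainly subjects who stayed on study, while a late scan from a withdrawing subject would not enter any by-visit row.

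The ADA exception shows that the SAP authors met the same problem. ADA has the same extension schedule as the laboratory panel (Weeks 24, 36 and 48), and for ADA the SAP looks forward to the next visit at which the test is done.

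**Working it through.** The plan states no figure on this point, so there is none to reproduce. The check is a count of visit slots.

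**Inputs**
- Post-Baseline visits to Week 48 (Table 5-1): Weeks 2, 4, 6, 8, 10, 12, then 16, 20, 24, 28, 32, 36, 40, 44 and 48. That is 6 + 9 = 15 slots.
- Laboratory visits: all six up to Week 12, then Weeks 24, 36 and 48.
- Post-Baseline PET visits: Weeks 12 and 48. The Baseline scan is 0 to 14 days before Baseline; the Week 12 scan is 0 to 14 days after the Week 12 visit.
- Assumptions: visits are attended up to withdrawal, so that an EW day maps to the next scheduled visit, and a withdrawal scan takes the slot of its EW visit.

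**Laboratory tests**
- Extension slots without a laboratory test: Weeks 16, 20, 28, 32, 40 and 44. Loss = 6/9 = 67%.
- By day, over days 85 to 336: 6 × 28 = 168 of 252 days = 67%.
- Over all post-Baseline slots: 6/15 = 40%. Up to Week 12: 0/6.

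**PET after a Week 12 scan**
- With the scan on day 84 + s (s = 0 to 14), a withdrawal scan requires an EW day later than 168 + s, that is, after about Week 24 to 26.
- Possible slots: Weeks 28, 32, 36, 40, 44 and 48. Only Week 48 is a PET visit. Loss = 5/6 = 83%.
- By day, s = 0: eligible days 169 to 336 = 168; the last 28 map to Week 48; dropped 140/168 = 83%.
- By day, s = 14: eligible days 183 to 336 = 154; dropped 126/154 = 82%.
- If the Baseline scan was 14 days before Baseline, EW days 71 to 84 also qualify. These 14 days map to Week 12 and are kept. The lowest share is then 126/(154 + 14) = 75%.
- Range over eligible withdrawal time: 75% to 83%.

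**Does another rule restore the data?**
- SAP 4.3 refers EW measurements back to 4.4. It neither rescues them nor adds a separate exclusion for them.
- The liver-abnormality table in SAP 11.3 counts subjects over all post-Baseline visits, so it may take in EW values. Read literally, 4.4 says they are listed only. The two sections conflict.
- The PET Per-Protocol Set (SAP 3.5.8) admits a subject on one evaluable post-Baseline scan. A subject could therefore qualify on a withdrawal scan that appears in no by-visit row.

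**Number of subjects**
- The documents forecast no withdrawal rate. Assuming 10-20% of about 25 substudy subjects: 2.5 to 5, so about 3-5 over the whole 48 weeks. Those withdrawing after about Week 24 with a PET-positive previous scan would be fewer.

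**The case against.** The strongest reply is that the consequences are narrower than the slot counts suggest. Much of it stands.

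- A reader might infer that EW data disappear. They do not: all values are listed, and the TEMA listing shows every measurement of a variable for any subject with one markedly abnormal result. AE and discontinuation tables may also capture the event. What is lost is the comparison by group.
- A reader might infer that subjects withdrawn for liver values vanish from the summaries. The documents do not support that, because the liver table is not restricted to scheduled visits. No such table covers neutrophils or lymphocytes. Even there, the value that triggers withdrawal will usually come from an earlier scheduled or unscheduled draw, not from the EW draw.
- A reader might multiply an assumed 10-20% withdrawal by 72 and report 7-14 subjects affected. That is the wrong base for PET. For laboratory tests it includes withdrawals up to Week 12, which lose nothing.
- Slots are not scans. That most withdrawal scans are dropped follows only if withdrawals are spread fairly evenly, and the documents give no timing.
- PET-MRI data are listed and kept out of the PET-CT summaries under SAP 8.3.6.2, whatever 4.4 says. The PET analysis is exploratory, and a late withdrawer's Baseline and Week 12 scans remain in the summaries.
- Table 5-1 and SAP 2.3 treat Week 48 and early withdrawal as one scan occasion, so a programmer might place the scan at Week 48. SAP 4.4 nonetheless tests the mapped visit, and 8.3.6.2 does not override it.
- The reason given for the ADA exception, matching first-positive counts to period totals, does not carry over directly to laboratory means. Moving a Week 16 value to Week 24 would misdate it by 8 weeks, so copying the ADA rule to laboratory data is a debatable trade-off.

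None of this gives an EW haematology value a TEMA row, or gives a withdrawal PET-CT scan mapped to Weeks 28 to 44 a summary row.

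**Conclusion.** The point holds in a limited form. SAP 4.4 is an explicit rule, not a missing detail, and it leaves collected safety and imaging data out of the by-visit summaries. The 67% laboratory loss applies to extension slots only. The 75-83% PET loss applies to eligible withdrawal time and rests on even timing and on visits being attended up to withdrawal. How many subjects this touches cannot be derived from the documents; the likely number is small.

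The documents do not support saying that these results never reach any summary, nor that the Week 48 bone-formation result is materially biased. They support saying that TEMA counts and PET-CT summaries can omit some EW results, and that 4.4 and the liver table in 11.3 need to be reconciled. Nothing here concerns the primary analysis.

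**What to change.** Leave the by-visit rows and the mapping rule as they are, and make three additions to the SAP:

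1. In the TEMA table (SAP 11.3), add a row per variable for any post-Baseline value, including EW and unscheduled values.
2. State in SAP 11.3 that the any-post-Baseline liver-abnormality table includes EW values, and cross-refer from 4.4 so that the two sections agree.
3. In SAP 8.3.6.2, add a separate row for the last post-Baseline scan, withdrawal scans included, to the PET-CT SUVauc and lesion-count summaries. List the study day of each scan.

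The cost is SAP wording and programming; the data are already collected. SAP section 1 requires an amendment for changes to analysis definitions before database lock, so the additions can be prespecified. The downside is that the last-scan row mixes scan times. Listing the study day makes that visible, and the unchanged Week 48 row keeps the fixed-time summary intact.

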## **4.5           Interim analyses and data monitoring**

### **4.5.1       Data monitoring committee**

The conduct of the study and monitoring of the safety data will be supervised by an independent DMC to optimize subjects' safety and to identify any safety signals. Full details of the composition and roles of the DMC will be provided in a separate DMC Charter.

The data to be reviewed by the DMC will be as detailed in the DMC Charter and will include unblinded safety data. The details regarding the outputs to be produced and the analyses to be performed will be provided in a separate DMC SAP.

### **4.5.2       Interim analyses**

Three unblinded informal IAs are planned for this study.

IA1 will be performed when approximately 45 subjects have completed the Week 4 visit.

IA2 will be performed when the last randomized subject not participating in the PET-MRI/PET-CT has completed the Week 12 visit at the end of the Treatment Period or has withdrawn prematurely from the study.

IA3 will be performed when the last randomized subject has completed the Week 12 visit at the end of the Treatment Period or has withdrawn prematurely from the study.

The purpose of the IAs is for key Sponsor personnel to review the results of the primary efficacy, selected secondary and other efficacy analyses and safety outcomes to facilitate additional Clinical Planning or Portfolio Management decisions.

All analyses and unblinding instructions will be pre-specified in the Interim Analysis SAP.

#### **4.6 Multicenter studies**

The data summaries and statistical analyses will not be performed by center.

#### **4.7 Multiple comparisons/multiplicity**

Not applicable.

#### **4.8 Use of an efficacy subset of subjects**

In order to investigate the impact on the efficacy analyses, the PPS will be used to evaluate the subset of subjects in the FAS with no IPDs.

#### **4.9 Active-control studies intended to show equivalence**

Not applicable.

#### **4.10 Examination of subgroups**

Not applicable.

### **5 STUDY POPULATION CHARACTERISTICS**

#### **5.1 Subject disposition**

The number and percentage of subjects who were randomized into the study (and into the PET-MRI/PET-CT substudy), subjects who completed or prematurely discontinued the study, as well as the primary reason for discontinuation will be presented by treatment group and for all subjects, based on the RS. A subject who completed the study is defined as a subject who completed all visits up to the last scheduled study visit, ie, Visit 18 (Week 64). An additional summary of subject disposition in the PET-MRI/PET-CT substudy will also be presented separately by treatment group and for all subjects, based on the RS.

In addition, disposition of subjects during the Treatment Period and Treatment Extension Period will be summarized separately. The number and percentage of subjects who completed Week 4 and Week 12 of the Treatment Period, or prematurely discontinued the study during the Treatment Period, together with the primary reason for discontinuation will be presented by treatment group. The number and percentage of subjects who completed Week 48 (ie, the Treatment Extension Period) or prematurely discontinued during the Treatment Extension Period, together with the primary reason for discontinuation will be presented by treatment group. A subject is defined as completing Week 4, Week 12 and Week 48, respectively, if adequate efficacy data are available in the database to calculate the primary efficacy variable at the respective visit.

The number and percentage of subjects who discontinued due to AEs will be separately summarized by treatment group and for all subjects, based on the RS. This will be used for European Union Drug Regulating Authorities Clinical Trials (EudraCT) reporting.

The number and percentage of subjects included into each of the analysis sets will be summarized by treatment group and for all subjects based on all subjects screened. Percentages will be based on the RS for the purpose of this summary.

Screen failure reasons will be summarized, based on all subjects screened. A listing of subjects who did not meet study eligibility criteria (including glossary) will also be presented for all subjects screened.

In addition, the following listings will be presented by treatment group:

- Subject disposition (ES [all subjects screened])
- Study discontinuation (RS)
- Visit dates (SS)
- Subject analysis sets (ES [all subjects screened])

The listing of subject disposition will include:

- the date of informed consent
- for subjects participating in the respective pharmacogenomics, pharmacogenetic and PET MRI/CT substudies: date of respective informed consent
- date and time of first and last dose of IMP
- date of premature study termination and primary reason (if applicable)
- date of final contact
- if applicable, the date and reason for premature unblinding

The listing of study discontinuation will include the reason for discontinuation and the number of days on IMP.

The number of days on IMP will be calculated as follows:

$$\text{Number of days on IMP} = (\text{Date of Last Dose Received} - \text{Date of First Dose Received}) + 1$$

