## **2.2 Study variables**

### **2.2.1 Efficacy variables**

#### **2.2.1.1 Primary efficacy variable**

The primary efficacy variable for this study is the change from Baseline in Ankylosing Spondylitis Disease Activity Score (ASDAS) at Week 12.

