### **4.2 Handling of dropouts or missing data**

#### **4.2.1 Efficacy data**

##### **4.2.1.1 ASDAS derivation**

If 1 component for the ASDAS is missing at a given visit, and the visit prior to the visit with the missing component data is not the Baseline or Screening visit, the following will apply: the missing component will be imputed by carrying the last observation for the given component forward, and the ASDAS will be calculated accordingly.

If no value is available for that component before the missing visit, or if the visit prior to the visit with the missing component data is either the Baseline or Screening visit, then the next observation will be carried backwards, and the ASDAS will be calculated accordingly.

If an unscheduled or repeat visit with non-missing data for the given ASDAS component is available and this visit is closer to the scheduled visit where the component data is missing, then the component data from the unscheduled/repeat visit will be used in the derivation of the ASDAS score.

If more than one component for the ASDAS is missing, ASDAS will not be calculated and treated as missing.

Any measurements of hs-CRP that are below 2 mg/L will be imputed with a fixed value of 2 mg/L for the purpose of deriving the ASDAS.

The statistical analysis will be performed based on the resulting derived values of ASDAS.

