### 4.3 Handling of repeated and unscheduled measurements

All repeated and unscheduled measurements will be presented in the data listings, where applicable. The following general rules will apply to all repeated and unscheduled measurements:

- For repeated measurements obtained prior to the first dose of IMP the latest value (which may be scheduled or unscheduled) will be used in the calculation of the descriptive statistics
- For repeated measurements obtained at the designated Baseline visit, the latest value (which may be scheduled or unscheduled) will be defined as the Baseline provided that this occurred prior to the first dose of IMP
- For repeated measurements obtained at any time point after the first dose of IMP, the values will not be included in the calculation of descriptive statistics or changes from Baseline.
- Unscheduled measurements performed for the Early Withdrawal (EW) visit will be assigned to the appropriate visit (Section 4.4) and analyzed accordingly

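### SAP 5.1 defines completing Weeks 4, 12 and 48 by whether ASDAS can be calculated, so the period rows for completed and discontinued subjects can overlap and can leave subjects out

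*SAP*

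**What the plan says.** SAP 5.1 summarises the two study periods separately. For the Treatment Period it gives the subjects who completed Week 4 and Week 12, "or prematurely discontinued the study during the Treatment Period, together with the primary reason for discontinuation will be presented by treatment group". For the Treatment Extension Period it sets completing Week 48 against discontinuing in that period. A subject completes Week 4, 12 or 48 "if adequate efficacy data are available in the database to calculate the primary efficacy variable at the respective visit". SAP 2.2.1.1 fixes that variable: "The primary efficacy variable for this study is the change from Baseline in Ankylosing Spondylitis Disease Activity Score (ASDAS) at Week 12". At Weeks 4 and 48 the rule can only mean the same change score at that visit.

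Two other rules decide whether an ASDAS exists at a visit.

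- **Early Withdrawal (EW) data.** SAP 4.3: "Unscheduled measurements performed for the Early Withdrawal (EW) visit will be assigned to the appropriate visit". Under SAP 4.4, EW assessments that do not fall on a scheduled day are "mapped to the nearest scheduled visit, relative to the Baseline visit date, following the last scheduled visit where assessments are available". Ties go to the earlier visit. "Assessments from the EW visit will be displayed as the mapped visit and will be flagged in the by-visit data listings".
- **Missing components.** SAP 4.2.1.1 imputes a single missing component. Beyond that: "If more than one component for the ASDAS is missing, ASDAS will not be calculated and treated as missing".

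Elsewhere the SAP treats completion as a matter of visits. In SAP 5.1 itself, completing the study means completing all visits through Visit 18. SAP 4.5.2 times the second and third interim analyses by subjects either completing the Week 12 visit or withdrawing early, as alternatives.

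**The concern.** A disposition table should place each randomized subject in one row per period. Here one row is defined by data availability and the other by study status, and nothing ties them together. A subject can satisfy both definitions or neither, so the two rows need not sum to the number randomized. At stake is the completed figure by arm for each period, which readers will take to mean that the subject stayed in the study to that visit.

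**Working it through.** The plan states no figure to reproduce. The check applies the rules literally.

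**1. What an EW visit collects.** Protocol 8.13 and SAP 4.4 give it the Week 48 assessments. Protocol 8.11 lists BASDAI, PGADA and hs-CRP among them, so all five ASDAS components are scheduled.

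**2. Which EW visits map to a period-ending visit.** SAP 4.4 places Week 6 at Day 42, so scheduled day = week × 7: Week 10 = Day 70, Week 12 = Day 84, Week 16 = Day 112, Week 44 = Day 308, Week 48 = Day 336.

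- *Last seen at Week 10.* The next visits are Days 84 and 112, with midpoint (84 + 112)/2 = 98, and the tie goes to the earlier visit. An EW visit on Days 71–98 maps to Week 12. Of these, Days 71–83 (13 days) precede the scheduled Week 12 day.
- *Last seen at Week 4, 6 or 8.* The midpoint between Weeks 10 and 12 is (70 + 84)/2 = 77, and the tie goes to Week 10. Days 78–98 map to Week 12, and Days 78–83 (6 days) precede Day 84.
- *Last seen at Week 44.* Days 309–335 (335 − 308 = 27 days) map to Week 48 before it is due.

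Protocol Table 5–1 allows ±3 days, so EW visits on Days 81–83 or 333–335 fall inside the visit window. Leaving them out, 10 days (71–80) remain for a subject last seen at Week 10, and 24 days (309–332) for one last seen at Week 44.

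**3. When an attended visit has no ASDAS.** The components are BASDAI Questions 2, 3 and 6, PGADA and hs-CRP. With 0 or 1 of the 5 missing, ASDAS is calculated; with 2 or more missing, it is not. One unanswered BASDAI removes 3.

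**4. Cross-classification at Week 12.**

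| Study status | ASDAS at Week 12 | Completed row | Discontinued row |
|---|---|---|---|
| Stayed | calculable | yes | no |
| Stayed | not calculable | no | no |
| Withdrew before Week 12 | calculable (EW mapped) | yes | yes |
| Withdrew before Week 12 | not calculable | no | yes |

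The second line is in neither row and the third is in both. The same table holds for Week 48 and the Treatment Extension Period.

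**5. A further open case.** SAP 2.3 has non-responders withdrawn at the Investigator's discretion without entering the extension. A subject withdrawn at the Week 12 visit with an ASDAS is a completer. Whether that subject also counts as discontinued in the Treatment Period is not stated.

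**6. Effect of one subject.** SAP 2.4 gives 2:1 randomization with at least 60 subjects, later at least 72.

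- CZP: 60/3 = 20, so 1/20 = 5.0 points; 72/3 = 24, so 1/24 = 4.2 points.
- Bimekizumab: 1/40 = 2.5 points; 1/48 = 2.1 points.

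**The case against.** **The mapping may not reach SAP 5.1.** SAP 4.4 governs EW results in descriptive summaries, and SAP 5.1 does not cite it. That stands as a caveat, since the overlap rests on reading the two together. But the disposition table is itself a descriptive summary, SAP 4.3 is general, and nothing excludes mapped data.

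**Data availability may be what was meant.** SAP 2.4 wants 60 subjects available at Week 12 to compare ASDAS change. A reader might infer that the completion rule undermines this commitment. It does not: a withdrawn subject with a mapped ASDAS may properly count as available for that comparison, and one without an ASDAS does not. But a count of that kind should be labelled as data availability, not set against discontinuation.

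**Retention remains readable.** A reader might infer that discontinuation or retention is misstated. Premature discontinuation, with its reason, is counted without reference to ASDAS, so retention can be taken as randomized minus discontinued. Only the completed row is at fault.

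**Week 4 is different.** Someone who withdraws after Week 2 with an EW visit mapped to Week 4 is wrongly labelled a Week 4 completer. That does not break the table, because completing Week 4 and discontinuing before Week 12 overlap legitimately.

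**Cases are few and traceable.** The overlap needs a Baseline ASDAS and at least four of five components at the EW visit. The omission needs two or more components missing and not supplied by an unscheduled or repeat visit; SAP 4.2.1.1 does not say which of those two rules applies first. Listings flag EW assessments and give visit dates and termination dates with reasons. All of this stands and keeps the point minor.

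**Conclusion.** The point holds as a defect in one descriptive table. The completed and discontinued rows for the Treatment Period and the Treatment Extension Period are neither mutually exclusive nor exhaustive, and the completed row can be too high or too low.

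This rests on the SAP 4.4 mapping applying to the disposition table, and on the component conditions given above. The number of subjects affected is unknown: any expected count would need a dropout rate and a pattern of withdrawal times that the documents do not supply. What can be stated is the effect per subject: 4.2 to 5.0 points for CZP and 2.1 to 2.5 points for bimekizumab.

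A reader might also infer that efficacy results are touched. The documents do not support that. The primary analysis uses the Per-Protocol Set and whether a Week 12 ASDAS exists (SAP 8.1.2), and the secondary variables are classified from ASDAS (SAP 8.2.1.1). Neither uses the completer label. Whether EW data should enter Week 12 efficacy summaries at all is a separate question about SAP 4.4.

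**What to change.** In SAP 5.1:

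1. Define completing Week 4, 12 or 48 as attending that scheduled visit without having discontinued the study before it. State that a visit mapped from an EW visit does not count. Derive this from the visit and study termination eCRF data.
2. State which row holds a subject who is withdrawn at the Week 12 visit for non-response.
3. Report ASDAS availability at each of these visits as a separate row. This keeps the data-availability count that the present definition gives.

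The cost is a sentence or two and one table row. No new data are needed, since SAP 5.1 already plans listings of visit dates, termination dates and reasons.
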